4.2.6. Maximum Tolerated Dose and Recommended Phase 2 Dose

The MTD is defined as the dose with the highest posterior probability of subjects experiencing a DLT in the first 28 days on treatment in the target interval [16%,33%], and for which the probability that the DLT rate lies within the excessive toxicity or the unacceptable toxicity windows is less than 25%. The interval boundaries of 16% and 33% are chosen to be consistent with the traditional 3+3 design toxicity boundary which is 1/6 and 1/3.

The RP2D will be MTD or a lower dose that provides adequate PK exposure and biologic activity with superior tolerability. Up to 12 additional subjects will be enrolled at the dose to further define the safety and tolerability of the dose and schedule. The RP2D may be different for mono-therapy and for the combination therapy with ATRA.

Data considered for RP2D selection will include, but not be limited to: safety, available PK profile, and observed signs of clinical activity from Part 1.

4.3. Part 2: Expansion Cohort

Once the respective RP2D have been determined, an expansion cohort of up to 30 subjects each, GSK2879552 mono-therapy or in combination with ATRA, will be enrolled in order to better characterize the clinical activity and safety profile of the RP2D.

Additional expansion cohorts may be initiated to test the efficacy of i) GSK2879552 at RP2D in ≥ 60 years old treatment naïve subjects, and ii) GSK2879552 in combination with other agents (demonstrated synergy in pre-clinical studies) in relapsed/refractory or ≥ 60 years old treatment naïve subjects.

The statistical design and number of subjects to be enrolled in the dose expansion cohort is based on the predictive probability of success if enrollment continues until all planned subjects are recruited [Lee, 2008]. The predictive probability design allows for evaluation of stopping rules after each subject once a minimum number of subjects are evaluable. In this particular study, we will stop only for futility. Final decisions on stopping enrolment will depend on the totality of the data collected.

4.4. Intra-subject Dose-Escalation

Intra-subject dose escalations may be considered on a case-by-case basis, provided that the subject has not experienced a DLT, and a higher dose level cohort has been cleared without a DLT.

Decision on intra-subject dose escalation will be made after review of all safety data and approval by a GSK Medical Monitor and discussion with the investigator.

Subjects approved for intra-subject dose escalation will require additional limited PK sampling at the higher dose as determined by GSK Clinical Pharmacology.

4.5. Study Treatment

4.5.1. Treatment Assignment

Subjects will be identified by a unique subject number that will remain consistent for the duration of the study, except for subjects who are allowed intra-subject dose escalation and start the treatment from Day 1 with the new subject numbers allocated to them.

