4.2.3. PK/PD Expansion Cohorts

Any dose level(s) in Part 1 may be expanded up to 12 subjects in order to collect adequate data on safety, PK or PD. However, PD sample (peripheral blood and bone marrow aspirate) collection may be stopped early at the sponsor's discretion. Subjects may be enrolled at previously completed dose levels for the purpose of obtaining additional data. These subjects may have the dose escalated to a higher completed dose level (not exceeding the maximum tolerated dose [MTD]) once the necessary PK/PD procedures have been completed.

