13.8.2. Safety Analyses

The All Treated Subjects Population will be used for the analysis of safety data. All serially collected safety endpoints (e.g. laboratory tests, vital signs, electrocardiogram [ECGs]) will be summarized according to the scheduled, nominal visit at which they were collected and across all on-treatment time points using a “worst-case” analysis. Complete details of the safety analyses will be provided in the Reporting and Analysis Plan (RAP).

Safety endpoints are described in Section 2. Complete details of the safety analyses will be provided in the RAP.

A listing by subject including treatment administered, and compliance, will be generated with dates and times of treatment administered. The number of subjects exposed to study drug will be tabulated for Part 1 (for each dose cohort) and Part 2.

All relevant safety data will be listed and summarized according to IDSL standards. The reporting and analysis plan will list the IDSL templates for the displays. Adverse events will be coded and grouped by system organ class (SOC) and preferred (coded) term (PT) using the Medical Dictionary for Regulatory Activities (MedDRA) system for adverse event coding. AEs will be graded according to the National Cancer Institute Common Terminology Criteria for Adverse Events (NCI CTCAE) Version 4.03. Adverse events will be summarized by maximum toxicity grade for each initial dose level. All AEs will be listed. A summary of the number and percent of subjects reporting each AE at least once will be produced for all AEs, for drug-related AEs and for SAEs for Part 1 (for each dose cohort) and Part 2. A listing of those AEs identified as dose-limiting toxicities will also be produced for each dose cohort for Part 1. A listing showing the relationship of AE

verbatim text to group terms and body systems will also be produced. A listing of withdrawals due to AEs will be provided. Deaths and SAEs will be listed should they occur.

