## 2. SUMMARY OF KEY PROTOCOL INFORMATION

### 2.1. Changes to the Protocol Defined Statistical Analysis Plan

Due to the early termination of the study 200200, this RAP is developed for an abbreviated CPSR. Since Part 2 cohort expansion was not initiated prior to study closure, no statistical analysis will be performed for Part 2.

Changes from the originally planned statistical analysis specified in the protocol are outlined in [Table 1](#).

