## 2.4. Statistical Hypotheses / Statistical Analyses

No formal statistical hypotheses are being tested. Analysis of the data obtained from this study will be focused on comparison between dose cohorts and only descriptive methods will be used in analysis of the data obtained from this study.

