## **6.6. Extent of Exposure**

Extent of exposure of GSK2879552, alone or in combination with ATRA will depend on tolerability of the subjects to the doses administered and the course of their disease. The number of subjects exposed to GSK2879552, alone or in combination with ATRA will be summarized for each dose level administered according to the duration of therapy. The duration of exposure to study treatment in weeks (from first day to last day of treatment plus) will also be summarised.

All the dose reductions, dose escalations and dose interruptions will be summarised and listed separately.

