## 7. SAFETY ANALYSES

The safety analyses will be based on the All Treated Subjects population, unless otherwise specified. All summaries will be presented by dose level.

Study population analyses will be based on GSK Core Data Standards. Details of the planned displays are presented in [Appendix 10](#): List of Data Displays.

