## 8. EFFICACY ANALYSES

All efficacy analyses will be based on the All Treated Subjects population unless otherwise specified. All analyses will be presented by dose of study treatment. Details of the planned displays are provided in [Appendix 10: List of Data Displays](#).

Response rate (RR) is defined as the percentage of subjects who achieved CR, CRp, PR or morphologic leukemia-free state (MLFS) among subjects who received at least one dose of treatment.

The investigator-assessed best response along with response rate (Without confirmation) will be summarized by dose of study treatment. A listing of investigator assessed responses (Without Confirmation) will be provided.

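### Do the differing dose-column wordings and the renumbering of dose escalators put their later adverse events and responses in conflicting columns?

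*Protocol*

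**What the plan says.** Protocol 4.4 allows escalation within a subject case by case. For the PK/PD expansion cohorts, Protocol 4.2.3 adds: "These subjects may have the dose escalated to a higher completed dose level". Under Protocol 4.5.1, repeated in SAP 2.3, a subject keeps one number "except for subjects who are allowed intra-subject dose escalation and start the treatment from Day 1 with the new subject numbers allocated to them".

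The dose column is worded differently from place to place:

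- Protocol 13.8.2: "Adverse events will be summarized by maximum toxicity grade for each initial dose level". The summary of subjects reporting each event at least once, in the same section, is by dose cohort in Part 1.
- SAP 7, safety: "All summaries will be presented by dose level".
- SAP 8, efficacy: "All analyses will be presented by dose of study treatment".
- SAP 6.6, for the number of subjects exposed: "will be summarized for each dose level administered according to the duration of therapy".

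SAP 5.1 lists eight display groups: 1, 2, 4, 8, 12 and 20 mg QD, 2 mg QD with ATRA, and 20 mg QD PK/PD expansion. SAP 2.4 states the aim: "Analysis of the data obtained from this study will be focused on comparison between dose cohorts". SAP 2.1 introduces its Table 1 with "Changes from the originally planned statistical analysis specified in the protocol are outlined in", and that table has no entry about dose columns.

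**The concern.** A person who takes two doses could belong to either of two columns. By initial dose, whatever happens after the increase counts at the lower dose. By dose taken, it counts at the higher one. The protocol names the first for worst-grade adverse events, while the SAP drops the word initial and does not list that as a change. Renumbering adds a further twist. If records are processed by subject number, the higher dose becomes the initial dose of the second number, so two people with the same course could sit in different columns, and one of them could be counted twice in overall totals.

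Adverse events are the Part 1 primary endpoint, and cohorts can be as small as one subject. One event that changes columns could reverse the apparent order of two doses in SAP Table 3.1 (events by maximum grade) or Table 2.1 (best response).

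**Working it through.** **What the columns are.** Three features of the SAP fit assigned cohort better than dose being taken.

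1. SAP 5.1 has two columns at 20 mg QD, one for escalation and one for expansion. Dose taken cannot separate them; cohort can.
2. Protocol 4.8.2 and 4.8.3 provide for reductions of at least 25%. A 25% cut from 8 mg is 8 × 0.75 = 6 mg, and from 4 mg it is 4 × 0.75 = 3 mg. Neither has a column in SAP 5.1, so displays by dose taken would leave some data with nowhere to go.
3. The mock exposure table (POP_T1, SAP 11.11) gives the mean and SD of average daily dose within each dose column. SAP 11.6.2 builds cumulative dose by adding days times daily dose within a subject. Both suit a person who stays in one column while the dose varies.

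On that reading, dose level in SAP 7 and initial dose level in Protocol 13.8.2 mean the same thing, and SAP Table 1 omits nothing. The SAP 6.6 wording on doses administered governs exposure only.

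**Whether adverse events and responses part company.**

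| Escalator | Adverse-event column | Response column |
|---|---|---|
| Same number, grouped by cohort | lower dose | lower dose |
| Renumbered, numbers linked, grouped by cohort | lower dose | lower dose |
| Renumbered, each number treated as a record | higher dose | higher dose |

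In the last row the new number's initial dose is the dose being taken, so all the wordings agree. A split arises only if the safety wording is read as the person's first dose and the efficacy wording as the current dose. The text permits that reading but does not call for it.

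**Size.** The plan states no figure that depends on this point, so the following is an illustration. Inputs are the cohort sizes in Protocol 1.3.5 at 20-NOV-2015: 1, 2, 7 and 1 subjects at 1, 2, 4 and 8 mg, or 11 people. Assume one person moves from 2 to 4 mg and has one event afterwards, and that nobody else has that event. Brackets are exact 95% limits.

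| Rule | 2 mg | 4 mg | Overall |
|---|---|---|---|
| (a) Person's initial dose | 1/2 = 50.0% (1.3 to 98.7) | 0/7 = 0% (0 to 41.0) | 1/11 = 9.1% |
| (b) Initial dose of the new number | 0/2 = 0% (0 to 84.2) | 1/(7+1) = 12.5% (0.3 to 52.7) | 1/(11+1) = 8.3% |
| (c) Dose taken at the event | 0/2 = 0% (0 to 84.2) | 1/(7+1) = 12.5% (0.3 to 52.7) | 1/11 = 9.1% |

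For a 4 to 8 mg move, (a) gives 1/7 = 14.3% and 0/1 = 0%, while (b) and (c) give 0/7 = 0% and 1/(1+1) = 50%. The order of the two doses does flip, but the 2 to 4 mg limits show how little such percentages carry under any rule. Rules (b) and (c) share a column and differ only in the overall denominator.

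The illustration is limited. Protocol 1.3.5 reports that all 11 subjects had adverse events, so the assumption of no other event can hold only for a single preferred term. The sizes of the later 12 mg, 20 mg, ATRA and expansion groups are not given.

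**The case for a change.** The best case for a change is that the two kinds of escalator may be treated differently. SAP Table 1.11 and Listing 14 display dose escalations. If every escalator were renumbered and records were processed by number, both would be empty, so escalation under one number seems to be expected as well. With initial dose applied number by number, a same-number escalator's late event goes to the lower dose and a renumbered one's to the higher, which is (a) against (b) above. A reset Day 1 could also make a toxicity carried over from the lower dose part of the SAP 5.2 baseline, and it could duplicate a person in the Enrolled and overall counts.

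The part that stands is that the SAP does not define its term for someone who took two doses, and does not say that two numbers belonging to one person are linked. The rest is conditional. It needs both kinds of escalator to occur and the programmer to ignore the link. Protocol 4.2.3 does not say how its escalators are numbered, and a planned table does not show that such subjects exist. SAP 4 defines Enrolled by participants who passed screening, which describes people and not numbers. A distorted Day 1 drug profile would require full sampling after the escalation, whereas Protocol 4.4 provides only for limited sampling at the higher dose.

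Choosing one rule is also no clear gain. Initial dose keeps cohorts intact but credits later toxicity to the lower dose. Dose at onset does the reverse and can count a persisting event at both doses.

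**Conclusion.** No change follows. The wording is uneven and one term is undefined, but no written rule sends an escalator's adverse events and responses to different columns. The column list in SAP 5.1 is best read as assigned cohort, which agrees with Protocol 13.8.2, and an analyst following it would produce sound descriptive tables.

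The most that could move is one person's events between two small columns, such as 1/2 and 0/7 against 0/2 and 1/8, and one record in an overall count of 11. No error rate, sample size or test depends on it. The SAP serves an abbreviated report of a terminated study whose Part 2 never began. Listings 11, 14, 15 and 40 give exposure, dose escalations, adverse events and responses subject by subject, so a reader can place any event at the dose taken.

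This rests on the assigned-cohort reading of SAP 5.1 and on a renumbered person's two numbers being recognised as one person. The documents give neither the number of escalators nor any renumbered subject.

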11. Symptomatic or untreated CNS leukemia. Subjects are permitted to enroll if previously treated for CNS disease, free of symptoms at the time of screening, and have not required intrathecal chemotherapy at least 1 month prior to study Day 1.
12. Cardiac abnormalities as evidenced by any of the following:
 - Clinically significant uncontrolled arrhythmias or uncontrolled hypertension.
 - History or evidence of current \geq Class II congestive heart failure as defined by New York Heart Association (NYHA, [Appendix 2](#)).
 - History of acute coronary syndromes (including unstable angina and myocardial infarction), coronary angioplasty, or stenting within the past 3 months.

- Baseline QTc interval using Fridericia's formula ≥ 450 msec or ≥ 480 msec in subjects with Bundle Branch Block. QTc value based on single or average of triplicate ECGs obtained over a brief recording period.
13. Administration of an investigational drug within 14 days or 5 half-lives, whichever is **shorter** with a minimum of 14 days preceding the first dose of study treatment(s) in this study.
 14. Have a known immediate or delayed hypersensitivity reaction or idiosyncrasy to drugs chemically related to GSK2879552 or LSD1 inhibitors that contraindicates their participation.
 15. Lactating female.
 16. Consumption of Seville oranges, grapefruit, grapefruit hybrids, grapefruit juice, pommelos, or exotic citrus fruits, from 1 day prior to the first dose of study treatment(s) until the last dose of study drug.
 17. Current use of a prohibited medication including anticoagulants or platelet inhibitors (Section 10.2) or expected to require any of these medications during treatment with the investigational drug.
 18. Previous treatment with GSK2879552

For ATRA Combination arm ONLY

19. Known hypersensitivity to ATRA, parabens (preservatives in the gelatin capsule) or other retinoids.
20. ATRA capsule contains sorbitol. Subjects with rare hereditary problems of fructose intolerance are excluded.
21. History of seizure within 12 months or brain tumor (primary)
22. History of taking mega-dose vitamin A ($>25,000$ USP U/day) within 3 months from the dosing start.

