An internal dose-escalation committee will be comprised of the following GSK representatives: Medical Monitor, Safety Physician or Scientist, Clinical Scientist, Biostatistician, PK and PD Scientists, and Study Operation Lead. The dose-escalation committee will review available relevant data on demographics, all adverse events including non-DLT toxicities, laboratory assessments, 12-lead ECGs, and dose administration logs, as well as PK data. Quality control of critical safety data will be described in the Dose Escalation Plan, which includes ongoing study monitoring visits, Sponsor review of the clinical database, and confirmation by site investigators and/or delegate that the data is accurate and complete.

On the basis of a review of these data and in joint discussions with the participating investigators, a determination will be made as to whether dose escalation/de-escalation should continue as recommended by the N-CRM. The dose-escalation decision and

rationale for each cohort will be discussed with investigators during teleconference(s) and documented in writing, with copies maintained at each study site and in the study master file.

Description of the Continual Reassessment Method

After each cohort, a dosing recommendation for the next cohort will be made using the N-CRM. All available data, including safety, PK and PD data from current and prior cohorts will be reviewed at the dose escalation meeting. Although the N-CRM will be used to recommend the next dosing level, clinical judgment by the Medical Monitor and internal dose-escalation committee in consultation with the investigators can halt or reduce dose escalation or de-escalate as deemed appropriate at any time during the trial.

The N-CRM design is a type of Bayesian adaptive dose escalation scheme that assumes a two-parameter logistic model for the toxicity rate based on dose. It is a modified version of the original Continual Reassessment Method (CRM) [O'Quigley, 1990]. A CRM-based design uses a statistical model for dose and toxicity, and is expected to locate the MTD efficiently while minimizing the number of subjects exposed to pharmacologically inactive dose levels.

The method is fully adaptive and makes use of all the DLT information available at the time of each dose assignment. In contrast, the 3+3 method only uses information from one dosing cohort at a time.

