13.4.2. Part 2: Expansion Cohort

The sample size and stopping rules are based on the methodology of Lee et al. [Lee, 2008]. The predictive probability design is similar to a Green-Dahlberg design in that it allows for early stopping for futility. The differences are that the predictive probability design allows for evaluation of stopping rules after each subject, rather than at only two stages, once a minimum number of subjects are evaluable. In this particular study, we will stop only for futility.

Bayesian statistics will be employed to calculate the predictive probability that the response rate is greater than the historic response rate at interim analyses using a weak/non-informative prior. A Bayesian analysis expresses uncertainty about a parameter in terms of probability. A prior distribution is defined to characterize the level of knowledge about a parameter before the data are collected. Once the data are collected, a posterior distribution is formed using the prior distribution and the observed data. A very weak prior Beta distribution with a mean response rate equal to the target response rate is assumed. Thus, the posterior distribution for the response rate will be primarily driven by the data and can be derived as follows:

Let p denote the response rate, the number of responses in the current n subjects, x , follows a binomial distribution, Binomial (n , p). Taking the Bayesian method and combining the prior distribution and the observed data x , the posterior distribution of the response rate follows a beta distribution, i.e.

In the following case, 30% is the target response rate.

$$p \sim \text{Beta} (0.03 + x, 0.07 + n-x) \text{ with the posterior mean } (0.03+ x)/(0.07 + n).$$

For each cohort, to test hypotheses:

$$H_0: RR \leq 10\%$$

$$H_A: RR \geq 30\%$$

When maximum sample size is 30, the design will have a Type I error (α) of 0.064 and 89% power with the probability of early termination is 0.88 when the treatment is futile and probability of early termination 0.084 when the treatment is effective (true RR=0.3). Futility analysis for each dose expansion cohort will begin when response data is available for at least 10 evaluable subjects. The dose expansion cohort may be stopped early for futility if the predictive probability of success (response rate \geq historical response rate) is less than 5%. Futility stopping rules are described below.

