Dosing	
 
In Part 1, in Cohort 1, a single subject will receive a dose of GSK2879552 1 mg once daily. The subject in Cohort 1 must complete a full 28 days of dosing, and the safety and PK data will be reviewed prior to starting Cohort 2.
 
Starting with Cohort 2 the dose escalation will continue using the Neuenschwander - continuous reassessment method (N-CRM).
 
Upon review of the safety, tolerability, clinical activity, PK, PD data, the RP2D or doses will be selected.
 
Subjects may be enrolled at previously completed dose levels for the purpose of obtaining additional PK or PD data.
 
In Part 2, once the RP2D has been determined, subjects will be enrolled at the RP2D and will be evaluated for safety and efficacy while monitoring the futility stopping rules.
 

Time & Events	
 
Refer to Protocol Amendment 5 Section 7.1 Time and Event Table(s)
 

Overview of Study Design and Key Features	
Treatment Assignment	Subjects will be identified by a unique subject number that will remain consistent for the duration of the study, except for subjects who are allowed intra-subject dose escalation and start the treatment from Day 1 with the new subject numbers allocated to them.
Interim Analysis	
 
• In Part 1, interim analyses to inform dose escalation will be performed following the completion of each monotherapy and combination dose cohort in part 1. The primary driver for dose escalation decisions in Part 1 will be governed by an N-CRM model for the mono-therapy dose cohorts and a Bayesian copula regression for the combination dose cohorts. They will be used to predict the probability of DLT at the dose levels yet to be tested to further guide these decisions.
 
• After the initial 10 evaluable subjects, have enrolled at the RP2D dose, response data will be reviewed on an ongoing basis and the number of responses observed will be compared with the stopping rules provided in Section 13.4.2 of Protocol Amendment 5.
 

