### 5.2. Baseline Definitions

- Baseline will be defined as the most recent, non-missing value prior to or on the first study treatment dose date.

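### Escalators who restart at Day 1 get a new subject number, and nothing links the two numbers or says which record enters which analysis

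*Protocol*

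**What the plan says.** Protocol 4.5.1 gives each subject one constant number, "except for subjects who are allowed intra-subject dose escalation and start the treatment from Day 1 with the new subject numbers allocated to them". SAP 2.3 carries the same rule: "Subjects will be identified by a unique subject number that will remain consistent for the duration of the study", with the same exception for those who "start the treatment from Day 1 with the new subject numbers allocated to them". The exception covers only escalators who restart at Day 1. Protocol 4.2.3 also lets PK/PD-expansion subjects escalate and does not mention renumbering.

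Protocol 4.4 allows escalation case by case, "provided that the subject has not experienced a DLT, and a higher dose level cohort has been cleared without a DLT". For the monotherapy dose-toxicity model, Protocol 4.2.1 says that it "makes use of all the DLT information available at the time of each dose assignment". Protocol 4.2.5 counts DLTs in the first 28 days of treatment and does not say whether that window restarts under a new number.

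Several SAP rules are keyed to a first dose. All Treated Subjects (section 4) means anyone with at least one dose. Study day (11.6.1) runs from the first dose date. Section 5.2 reads: "Baseline will be defined as the most recent, non-missing value prior to or on the first study treatment dose date". The notes for Tables 3.7 to 3.10 ask for laboratory results by dose and overall. Exclusion 18 in Protocol 3.2.2 bars "Previous treatment with GSK2879552".

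**The concern.** Under these rules a renumbered escalator can look like a new person. The second number has its own first dose date, Day 1, baseline and place in All Treated Subjects. The second record is correlated with the first, because it is the same person. It is also selected, because Protocol 4.4 admits only people who have had no DLT. An N-CRM likelihood that treats it as a fresh independent subject borrows tolerance already shown in the first period.

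The safety tables matter most, because they are still to be produced for the abbreviated report. Dose-dependent thrombocytopenia is named as the primary toxicity (Protocol 1.4.5.1), and the haematology tables count increases over baseline grade. If baseline is itself an on-drug value, a drug-induced fall can disappear from the escalated record.

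**Working it through.** **The plan's own figures.** The only operating characteristics tied to a count of independent subjects are those for Part 2 (Protocol 13.4.2). An exact binomial recursion through the Figure 3 boundaries, with success at 6 or more of 30, gives type I error 0.0637 (stated 0.064), power 0.891 (89%), and early termination 0.882 at a 10% response rate (0.88) and 0.084 at 30% (0.084). They reproduce with 30 independent persons.

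**Baseline.** Protocol 4.8.3 takes Grade 4 thrombocytopenia as platelets below 25,000/mm³. Grade 4 platelets alone are not a DLT: Protocol 4.2.5 also requires low neutrophils and a hypoplastic marrow for at least 42 days after drug cessation. A person can therefore be at Grade 4 and still be eligible to escalate. Suppose platelets are 40,000 before any drug and 20,000 at the restart (illustrative values).

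| Baseline taken from | Baseline platelets | Can the escalated period show an increase to Grade 4? |
|---|---|---|
| Person's first ever dose | 40,000 (below Grade 4) | Yes |
| First dose under the new number | 20,000 (Grade 4) | No, already Grade 4 |

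**Overall columns.** With N persons, m of them renumbered, a events counted once per person and d repeat counts, a per-number percentage is (a + d)/(N + m) instead of a/N. For scale, Protocol 1.3.5 reports treatment-related Grade 4 thrombocytopenia in 2 of 11 subjects, or 18.2%. With m = 2 (assumed), the per-number figure runs from 2/13 = 15.4% (no repeat) to 4/13 = 30.8% (both repeat). Within a single dose column a person appears once, so those columns are not double counted.

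**N-CRM.** Inputs: the Appendix 1 prior (alpha −1.6278, SD 1.3652; ln beta −0.0116, SD 0.4136; correlation 0.2429), reference dose 5 mg (Protocol 4.2.1), and Table 6 data of 0/1, 0/2, 0/4 and 0/1 DLTs at 1, 2, 4 and 8 mg. The model is logit p(d) = alpha + beta·ln(d/5), integrated on a grid. Adding k DLT-free second-period records at 8 mg (k is an assumption) gives these values of P(DLT rate ≥ 33%):

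| k | 8 mg | 15 mg | 20 mg |
|---|---|---|---|
| 0 | 0.083 | 0.247 | 0.335 |
| 1 | 0.055 | 0.200 | 0.284 |
| 2 | 0.036 | 0.162 | 0.243 |
| 4 | 0.016 | 0.108 | 0.179 |

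The limit is 25%. Two added records bring 20 mg under it and move the admissible dose with the highest target-interval probability from 15 to 20 mg. Table 6 holds only 1 + 2 + 4 + 1 = 8 subjects, which is why one or two records matter.

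**PK.** Protocol 1.3.4 gives a terminal half-life of 12 to 38 hours, and no washout before a restart is stated. Twenty-four hours after a dose the fraction left in the terminal phase is 0.5^(24/12) = 25% to 0.5^(24/38) = 65%. A renumbered Day 1 need not be a single-dose profile. It could still enter the Day 1 dose-proportionality, accumulation and time-invariance analyses (SAP 9.1.3), where the random effect is the subject.

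**The case against.** The strongest reply is that no passage says both records are analysed as independent subjects. A reader might infer it from the new number, but the documents do not support it as a statement of fact, and some text points the other way. Adverse events are summarised by initial dose level (Protocol 13.8.2). Escalations are tabulated as dose changes within subjects (SAP 6.6, Table 1.11, Listing 14). Protocol 4.4 asks only for limited extra PK sampling. The 28-day DLT window, read per person, excludes a second period. The sentence about using all DLT information contrasts the method with 3+3; it is not a data-inclusion rule. All of this stands against the strong reading. It does not close the gap: under a new number the initial dose is the higher dose, and a renumbered person need not appear as an escalation at all.

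A reader might also infer that renumbering makes an excessive dose materially more likely to pass. The rules do not bear that out in the scenario checked. Assume true DLT rates of 20% at 8 mg and 40% at 12 mg, no DLTs at 1, 2 and 4 mg as in Table 6, six subjects at 8 mg, and four new plus up to three renumbered subjects at 12 mg. With renumbered subjects admitted only if the four new ones were DLT-free (one reading of the clearance condition in Protocol 4.4), the chance that 12 mg meets the 25% rule is 0.425, 0.427 and 0.431 at within-person correlation 0.3, 0.5 and 0.8. With the four new subjects alone it is 0.434. An apparent rise, to about 0.45 at correlation 0.5, comes only from ignoring that condition.

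Finally, a loss of Part 2 power is tempting to claim, because Part 1 data at the RP2D may be pooled (Protocol 13.7.2). Part 2 was never started and will not be analysed (SAP 2.1), so this concerns the planned design only.

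**Conclusion.** The point stands as a gap created by an explicit rule. Both documents assign a second number, neither links it to the first, and the SAP's first-dose rules, applied per number, can give an on-drug baseline and a double count in the overall safety columns. These tables are still to be produced, so it is worth correcting before reporting.

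The size is unknown, because the number of renumbered subjects is not given; it could be none. The N-CRM figures show how sensitive a sparse model is to one or two added DLT-free records at 8 mg. They do not show that such records were added or that a wrong dose was chosen. The 100% cap on dose increments and the committee's power to halt or de-escalate (Protocol 4.2.1) also limit the next step, although the MTD definition in Protocol 4.2.6 uses the same 25% rule. The conflict with exclusion 18 arises only if a restart under a new number counts as a new enrolment, which the documents do not settle.

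**What to change.** - In Protocol 4.5.1 and SAP 2.3, keep one person-level identifier throughout, or carry a permanent link between the two numbers.
- In SAP 5.2, define baseline as the last value before the person's first ever dose of GSK2879552.
- In SAP section 4 and the table notes, count each person once in All Treated denominators and overall columns, at the first assigned dose, and show post-escalation data separately.
- State that a second period does not enter the N-CRM as a new independent subject, and that its events are still shown to the dose-escalation committee.
- In SAP 9.1.3, make the person, not the subject number, the random effect.
- Reconcile Protocol 4.5.1 with exclusion 18.

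The cost is wording in two documents and one linking variable in the analysis datasets. The downside is slightly fewer nominal records at the higher dose levels.
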